As mentioned above, sitagliptin exerts a potent and rapid anti-inflammatory effect as reflected in the suppression of ROS generation and intranuclear NF κ B binding(55). In association with this action, we also observed the suppression of the expression of SOCS-3, a protein whose expression is induced by the pro-inflammatory cytokines, TNF α , IL-1 β and IL-6 and which interferes with insulin signal transduction. This interference occurs at the IRS-1 level. The expression of SOCS-3 has been shown to be increased in the obese and is related to BMI and HOMA-IR, NF κ B activity and TNF α expression(56). Furthermore, SOCS-3 is also induced by a high fat high carbohydrate meal in parallel with the increased expression of TNF α and IL-1 β (57). More recently, it has been shown that weight loss following gastric bypass surgery is associated with a reduction not only in inflammatory indices but also that of SOCS-3 expression (58). Protein phosphotyrosine phosphatase-1B (PTP-1B) is another key protein which dephosphorylates proteins and interferes with insulin and leptin signaling and is also induced by the HFHC meal (59, 60). Indeed, a recent study has shown that Sitagliptin treatment for 6 weeks in patients with type 2 diabetes increases insulin sensitivity by 10% (measured as oral glucose insulin sensitivity during a meal test) (61). The same study also showed that Sitagliptin decreases endogenous glucose production in fasting as well

as post-prandial state by ~5%. While the effect of Sitagliptin on endogenous glucose output is probably caused by glucagon suppression, the mechanism underlying its insulin sensitizing effect is not known.

On the basis of the above, we suggest that sitagliptin and other DPP-IV inhibitors like linagliptin could potentially increase insulin signal transduction and increase insulin sensitivity by suppressing inflammatory mediators of insulin resistance including SOCS-3 and PTP-1B.

[figure not shown]
Therefore, in a study directed to investigate the potential anti-inflammatory effect of linagliptin, we would like to also test whether linagliptin exerts an insulin sensitizing effect. The methodology used will be based on the measurement of insulin sensitivity by hyperinsulinemic euglycemic clamps before and after the institution of linagliptin treatment in patients with type 2 diabetes.

Rationale for study

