Figure 3: Change in CRP (A), FFA (B) and IL-6 (C) concentrations following placebo and Sitagliptin 100mg daily for 12 weeks in type 2 diabetic subjects. N=12 each, data are presented as mean \pm SE. (*, **: $P<0.05$ by RMANOVA (compared to baseline) in sitagliptin and placebo groups, respectively, #: $P<0.05$ by Two-way RMANOVA compared to control groups.)

[figure not shown]

Figure 4: Representative Western blot and percent change in protein levels of JNK-1 after 12 wk of placebo and sitagliptin (100 mg/d) treatment in MNC of obese type 2 diabetic subjects (n = 10 and 12, respectively). Data are presented as mean \pm SE. *, $P < 0.05$ by RMANOVA (compared with baseline); #, $P < 0.05$ by two-way RMANOVA compared with placebo groups.

Study Hypothesis and Aims

Hypothesis 1: Linagliptin treatment suppresses basal and meal induced oxidative and inflammatory stress in mononuclear cells (MNC) and adipose tissue of obese patients with type 2 diabetes.

Aim 1.1: To compare reactive oxygen species (ROS) generation by MNC, protein expression of p47^{phox} subunit of NADPH oxidase, in MNC's and adipose tissue prior to and following 12 weeks of linagliptin or placebo.

Aim 1.2: To compare intranuclear NF κ B binding and the expression of JNK-1, TLR-4, TLR-2, CD26 and TNF α in mononuclear cells (MNC) and adipose tissue before and following 12 weeks of treatment with linagliptin or placebo.

Aim 1.3: To compare plasma hs-CRP and IL-6 concentrations and oxidized lipids in plasma (TBARS) and in urine (F₂-isoprostane) of obese type 2 diabetic patients prior to and following 12 weeks of linagliptin or placebo.

Aim 1.4: To compare post prandial (after a HFHC meal) changes in ROS generation, NF κ B binding and the expression of JNK-1, TLR4, TLR-2 IL-1 β and TNF α in MNC and adipose tissue prior to and following 12 weeks of linagliptin and placebo.

Hypothesis 2: Linagliptin **acutely** suppresses oxidative and inflammatory stress in mononuclear cells (MNC) of obese patients with type 2 diabetes.

Aim 2.1: to study the effect of single dose of linagliptin or placebo on oxidative stress and inflammatory mediators listed in Aim 1.1, 1.2 and 1.3 in MNC from obese type 2 diabetic patients.

Hypothesis 3: Linagliptin is an insulin sensitizer

Aim 3.1: To compare the glucose uptake induced by hyperinsulinemic-euglycemic (HE) clamp prior to and following 12 weeks of linagliptin or placebo.

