Aim 3.2: To compare the endogenous glucose output and suppression of endogenous glucose production by insulin during HE clamp prior to and following 12 weeks of linagliptin or placebo.

Aim 3.3: To compare mRNA and protein expression of SOCS-3 and PTP-1B, two important insulin resistance inducers, in MNC and adipose tissue prior to and following 12 weeks of linagliptin or placebo.

Hypothesis 4: Linagliptin increases post-prandial GLP-1, GIP and c-peptide concentrations.

Aim 4.1: To measure GLP-1, GIP and c-peptide concentrations following HFHC meal prior to and following 12 weeks of linagliptin or placebo.

RESEARCH DESIGN AND METHODS

RESEARCH DESIGN:

This is a prospective, **randomized, placebo -controlled, double blind** trial. The study will be conducted at the Diabetes – Endocrinology Center of Western New York under the direction of [name], M.D.

STUDY POPULATION:

Forty type 2 diabetic patients in the age group of 20 – 80 years will be recruited into the study. An informed consent will be obtained. They will be randomized into 2 groups: placebo and 5 mg/day linagliptin for 12 weeks

INCLUSION CRITERIA:

- Age 20-80 years inclusive.
- Type 2 diabetes
- $BMI \geq 30 \text{ kg/m}^2$
- Subjects on statins, ACE inhibitors, thiazolidinediones and antioxidants will be allowed as long as they are on stable doses of these compounds and the dosage is not changed during the course of study.
- $\text{HbA1c} \leq 7.5\%$

EXCLUSION CRITERIA:

- Use of GLP-1 agonists or DPP-IV therapy in the last 3 months.
- History of Pancreatitis.
- Risk for pancreatitis, i.e., history of gallstones, alcohol abuse, and hypertriglyceridemia.
- Subjects who are taking antiplatelet or anticoagulant medications will be excluded from the fat biopsy portion of the study.
- Coronary event or procedure (myocardial infarction, unstable angina, coronary artery bypass, surgery or coronary angioplasty) in the previous four weeks
- Hepatic disease (liver function tests more than 3 times the upper limit of normal)
- Renal impairment (serum eGFR <30 ml/min)
- Any other life-threatening, non-cardiac disease
- Uncontrolled hypertension (BP > 160/100 mm of Hg)
- Congestive Heart Failure class III or IV.
- Use of an investigational agent or therapeutic regimen within 30 days of study

- Participation in any other concurrent clinical trial

STUDY DESIGN:

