an infusion at the rate of 80mU/m². 20% glucose infused through the cephalic vein will be started at 5 minutes and glucose infusion rate will be titrated to maintain blood glucose concentration at the fasting glucose level in the obese and at 5.5mmol/l in T2D. Plasma samples for titrated glucose will be obtained at 10 minute intervals starting 30 minutes before the clamp, to quantitate rates of whole body glucose disposal and suppression of endogenous (primarily hepatic) glucose production. Blood sample will be collected for insulin and free fatty acids (FFA) concentrations every 30 minutes during the clamp. Calculations will be done using Steele's equation(67).

Calculations: Under steady-state postabsorptive conditions, the rate of endogenous glucose appearance (Ra) will be calculated as the $3[{}^3\text{H}]$ glucose infusion rate (disintegrations per minute per minute) divided by the steady-state plasma $3[{}^3\text{H}]$ glucose-specific activity (disintegrations per minute per milligram). During the euglycemic insulin clamp, the rate of Ra will be calculated using Steele's equation, using a distribution volume of 250 ml/kg. Endogenous (primarily hepatic) glucose production (EGP) will be calculated by subtracting the mean exogenous glucose infusion rate during the last 60 minutes (after steady state has been achieved) from Ra. The rate of insulin-mediated total body glucose disposal (Rd) will be determined by adding the rate of residual EGP to the exogenous glucose infusion rate. Insulin sensitivity will be expressed as Rd/lean body mass.

10. **Fat aspiration procedure:** Subjects who are taking antiplatelet or anticoagulant medications will be excluded from the fat biopsy portion of the study. Subcutaneous fat tissue aspiration will be performed on abdomen at a 10 cm distance from umbilicus. The skin will first be prepared and a sterile drape will be placed around the appropriate area. Under local anesthesia, 500mg-3g of fat tissue will be obtained. The adipose tissue will be centrifuged to remove blood and fluid contaminants. The upper adipose tissue will be collected into a separate sterile tube, washed twice with cold sterile Phosphate Buffered Saline (PBS) and centrifuged to remove the PBS. Total RNA, nuclear extracts and total cell lysates will be prepared from the adipose tissue.

DATA ANALYSIS

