Justification of drop-out rate: The analysis will adjust for only one baseline covariate: baseline medications. Two other covariates are change in BMI (which is not expected with linagliptin or placebo) and change in HbA1c. Sulfonylureas, metformin and subcutaneous insulin are not likely to induce insulin sensitization or decrease inflammation. Subjects currently on GLP-1 agonists or DPP-IV inhibitors will be excluded from the study. Thiazolidinediones can induce insulin sensitization as well as decrease inflammation. The use of thiazolidinediones should be equally distributed among the two groups. Less than 20% of our research subjects are on thiazolidinediones. Therefore it is likely that adjustment for thiazolidinediones should decrease sample size by <5%. Based on this justification and on our previous experience in diabetes trials, we have estimated that our drop-out rate will be 15% of 20 patients (3 patients per group).

The secondary endpoints for the study will be comparison of the relative change from baseline in a) inflammatory mediators in serum and adipose tissue, b) single dose effect of linagliptin on inflammation and oxidative stress, c) HFHC induced inflammation in serum and adipose tissue and d) insulin sensitivity and hepatic glucose output; before and after using Linagliptin for 12 weeks.

FACILITIES

LABORATORY: The Diabetes-Endocrinology Center of Western New York Research Laboratories at SUNY at Buffalo, contain 6 laboratories with space totaling approximately 1600 Qs ft designated for research purposes. These labs are dedicated for the P.I. research. There is a cold room, dark room and four labs have fume hoods. In addition, six offices (600 Qs ft) are attached to the labs for lab staff.

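### Relative change, with formula and baseline undefined, is an unsuitable scale for the two secondary quantities that are differences: the meal-induced response and residual glucose production in the clamp

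*Combined protocol and SAP*

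**What the plan says.** The last paragraph of DATA ANALYSIS puts all secondary endpoints on one scale: "The secondary endpoints for the study will be comparison of the relative change from baseline in" items (a) to (d). The last two items are "c) HFHC induced inflammation in serum and adipose tissue and d) insulin sensitivity and hepatic glucose output". No formula is given, and the denominator is not named.

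Elsewhere the plan says:
- **Clamp EGP** (Laboratory Procedures, item 9, Calculations): EGP "will be calculated by subtracting the mean exogenous glucose infusion rate during the last 60 minutes (after steady state has been achieved) from Ra". Aim 3.2 is "To compare the endogenous glucose output and suppression of endogenous glucose production by insulin during HE clamp".
- **Meal response** (Aim 1.4): "To compare post prandial (after a HFHC meal) changes in ROS generation" and in other markers, before and after 12 weeks. STUDY DESIGN limits this to 12 patients per group.
- **Baseline** has two meanings. In STUDY DESIGN it is the pre-treatment visit. In the meal challenge description it is the pre-meal sample of that visit.
- **Expected drug effect** (Hypothesis 1): "Linagliptin treatment suppresses basal and meal induced oxidative and inflammatory stress in mononuclear cells (MNC) and adipose tissue".
- **Model**: an analysis of covariance with medications, BMI change and HbA1c change. The pre-treatment value of the endpoint is not among the covariates. Transformations are left optional, and nothing covers a zero or negative denominator.

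**The concern.** A ratio to baseline works when the baseline is well above zero and fixed before treatment. A meal-induced response is a post-meal value minus a fasting value. Residual clamp EGP is what remains when one large rate is subtracted from another, under an insulin infusion meant to suppress it. Either can be small, zero or negative in an individual patient. A few such patients can then dominate the arm mean, and a real fall can score as a rise. A log transformation cannot repair non-positive values.

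If the denominator is instead each visit's own fasting sample, the week-12 denominator is a post-treatment value that the trial expects to move. At stake are the meal part of Hypothesis 1 (Aim 1.4, 24 patients) and the EGP-suppression part of Hypothesis 3 (Aim 3.2). With the formula open, the scale could also be chosen after the results are seen.

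**Working it through.** **The plan's own figure.** No sample size or power is stated for a secondary endpoint. The primary calculation reproduces: difference 24, SD 24, alpha 0.05 (two-sided assumed) and power 0.80 need 16.7, so 17 per group, and 17/0.85 = 20. It does not bear on this point.

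**Inputs.** From the documents: 12 per arm for the meal test; 20 per arm for the clamp, 17 after 15% drop-out; the 24% JNK-1 fall with sitagliptin, borrowed as an example of a basal effect. All meal and EGP levels and SDs below are assumptions, because the documents give none.

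**1. Pre-treatment meal increment as denominator.** For a normal increment with mean 30, P(increment ≤ 0) = Φ(−30/SD), and P(at least one among 24) = 1 − (1 − p)^24. At SD 20, p = Φ(−1.5) = 0.0668, so 24 × 0.0668 = 1.6 patients are expected and the chance of at least one is 81%. Power is by simulation with two-sample t-tests, visit correlation 0.5 and a true fall of 15 (50%):

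| SD of rise | Any denominator ≤ 0 among 24 | Power, relative change | Power, absolute change |
|---|---|---|---|
| 8 | 0.2% | 98% | 99% |
| 10 | 3% | 87–88% | 94% |
| 15 | 42% | 35% | 65% |
| 20 | 81% | 12–13% | 42% |

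Ranges are simulation noise between runs. At SD 20 the relative-change estimate has the wrong sign in about 28% of trials, against about 4% for absolute change.

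A second set-up (mean 30, between-patient SD 15, measurement SD 10, fall 15, 12 per arm) also shows the value of a covariate. Power is 25% for relative change, 70% for absolute change, and 75% for the week-12 value adjusted for the pre-treatment value.

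**2. Pre-treatment clamp EGP as denominator.** Assume Ra 6 mg/kg/min measured with 5–8% error and between-patient SD 0.3–0.5. Then SD = √(SD_between² + (error × 6)²). Example: √(0.3² + 0.3²) = 0.424, and Φ(−0.3/0.424) = 24%. Power uses 17 per arm, both SDs 0.3 and a true fall of 0.3:

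| Mean residual EGP | Share ≤ 0 | Relative change | Absolute change | Week 12, adjusted for pre-treatment |
|---|---|---|---|---|
| 0.3 | 24–33% | 4% | 52% | 62% |
| 0.6 | 8–19% | 11% | 52% | 62% |
| 1.0 | 1–8% | 31% | 52% | 62% |

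With a mean far from zero (2.0, SDs 0.3 and 0.2) the three analyses give 86%, 85% and 89%, so the problem disappears.

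**3. Each visit's own fasting sample as denominator.** Set pre-treatment fasting to 100 and the rise to 30, so the percent rise is 30%. Let fasting fall 24%, to 76.
- Rise unchanged at 30: 30/76 = 39.5%.
- Rise also cut by 24%, to 22.8: 22.8/76 = 30.0%.

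The first looks like a larger meal response on drug, the second like no change. Basal and meal effects are mixed.

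**4. Other readings.** Week-12 post-meal level over pre-treatment post-meal level has a sound denominator but also mixes the two effects. Expressing every sample from both visits relative to the one pre-treatment fasting sample has a positive, untreated denominator and still lets the increment be isolated.

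**The case against.** The strongest reply is that the plan never says it will divide by an increment. Its wording also covers the last reading in step 4, which is sound. This stands: a reader might infer that these endpoints are bound to fail, and the text does not support that. It leaves sound and unsound formulas equally open. What remains is that a ratio scale is stated for two difference quantities without the definition that would make it safe.

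Three further points stand.
- A reader might infer that all of item (d) is affected. It is not. Post-absorptive Ra is tracer infusion rate over specific activity, which is strictly positive. Relative change is workable there, for Rd per lean body mass and for mediator levels. Item (d) does not say whether hepatic glucose output means the basal or the clamp value.
- A reader might infer from step 3 that the scale is biased against linagliptin. That is partly a choice of scale: if fasting and rise both fall 24%, an unchanged percent rise truthfully reports no meal effect beyond the basal one.
- The power losses depend on assumed spreads. At SD 8 the loss is about one point.

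The laboratory outputs also include densitometry and normalised expression, so indexing to a reference sample is reasonable. The question is which sample.

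**Conclusion.** The concern holds in limited form. Relative change with an undefined formula and baseline is unsuitable for the meal-induced response in (c) and for residual clamp EGP in (d). That follows from how the two quantities are built and needs no assumed values.

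The size does need them. For the meal response the cost ranges from negligible (98% against 99% power at SD 8) to severe (about 13% against 42% at SD 20). For clamp EGP it is large if the mean residual is about 1.0 mg/kg/min or less with the assumed errors, and absent if it is well above zero. The documents do not show where this trial lies, so no particular loss of power can be claimed. These are secondary endpoints without a stated power. The primary JNK-1 endpoint and the 20 per group are unaffected. The plan should still be changed, before unblinding.

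**What to change.** State the formula and the baseline for each secondary endpoint.

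- **Meal response (c).** Express all of a patient's samples from both visits relative to the pre-treatment fasting sample (Visit 1B). Compare arms on the week-12 meal increment on the absolute scale, with the pre-treatment increment as covariate. Pre-specify one summary: for example incremental AUC over 0–5 h for serum and MNC markers, and 5 h minus 0 h for adipose tissue. Cover both serum and MNC, since item (c) names serum while Aim 1.4 names MNC.
- **Residual clamp EGP (d).** Compare the week-12 rate on the absolute scale, with the pre-treatment rate as covariate. Say whether hepatic glucose output means basal EGP, clamp EGP or both.
- **Strictly positive quantities.** Keep relative change, or a log ratio, for basal EGP, Rd per lean body mass and mediator levels.

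This changes analysis wording only: no added visits, samples or patients. The small cost is that the two results are no longer quoted as a simple percent change.
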